#### **7.5 Adherence to randomisation**

Vaccine will be given according to the randomization list. Subjects will not be able to choose between GSK or Baxter vaccines.

#### **7.6 Code break**

Should both vaccines arrive at each centre prior to regulatory approval and GSK and Baxter vaccines be allocated randomly, the Principal Investigators will be provided with a sealed envelope containing individual code-break envelopes for each subject. These would be opened in a medical emergency only should a serious adverse reaction (SAE) occur, defined as: requiring medical intervention; frank myonecrosis; ulceration, superinfection or phlebitis at the injection site; extreme pain or tenderness with complete limitation of use of arm; or severe intractable headache requiring repeated narcotic treatment. In the event of such reactions, the investigators will notify the Sponsor immediately and document the event in the Case Report Form (CRF).

#### **7.7 Vaccination compliance**

The site Principal Investigator will be responsible for adequate and accurate accounting of vaccine usage. The investigator or designee will administer the study vaccines only to individuals included in this study following the procedures set out in this study protocol. The date and time of vaccinations will be recorded. The investigator or delegate will track vaccines received, used and wasted and will retain all unused or expired products until it has been established that all accountability records are correct. Thereafter, all unused vaccines will be returned to the Department of Health or destroyed at the investigational site. An overall summary of vaccines supplied, received, wasted, used, and returned, re-assayed, or destroyed will be prepared at the conclusion of the study.

### **8.0 STUDY PROCEDURES**

#### **8.1 Clinical procedures**

Informed consent must be obtained from the subject, or where applicable, the subject's legally acceptable representative(s) prior to the performance of any trial specific tests or evaluations, i.e., any unusual or non-routine procedures that involve risk, however trivial, to the subject.

The following procedures will be done during Visits 1 to 8:

#### **Visit 1: Day 0: Screening and first vaccination**

1. Subjects will be enrolled providing they meet inclusion and exclusion criteria and give fully informed, written consent.
2. For females of childbearing potential, perform a urine pregnancy test.

3. If the subject meets all the inclusion criteria and none of the exclusion criteria, assign a study subject number relevant to the subject's age and study centre (for further information please refer to paragraph 7.4.).
4. Obtain basic demography, including age, sex, ethnicity, previous influenza vaccination (past three seasons), and influenza-like illness (since May 2009).
5. Obtain and record significant medical history.
6. Record any current medications taken. Verify if the subject has taken an analgesic/antipyretic medication on Day 0 prior to study vaccination. Document this information on the subject's appropriate CRF.
7. Collect 10ml clotted blood pre-immunisation for baseline antibodies. Process blood and store serum for serology assays as described in section 8.2.
8. Record oral temperature.
9. The vaccine administrator will give vaccine according to the randomisation list (if GSK and Baxter vaccines are both available) by IM injection in the deltoid muscle of the upper non-dominant arm.
10. Examine the site of injection of the vaccine for local reactions at the end of 30 minutes. These findings and any systemic reactions will be recorded on the appropriate CRF page.
11. Instruct each subject in the evaluation of local and systemic reactions (e.g. how to measure the maximum diameter of induration and erythema in millimetres at the injection site and how to record temperature with a thermometer). As a guide for subsequent evaluations, enter the findings from the 30-minute post-injection evaluation onto the subject diary card.
12. Give the subject diary card and thermometer for immunisation reactions to subjects and instructions for its completion. Tell subjects to:
  - Complete the diary at approximately the same time each day;
  - Notify study personnel immediately if the subject experiences a SAE. Serious adverse events are defined in Sections 1.2 and 8.5
  - Return the diary card to the site on the Day 7 visit.
13. Schedule the Day 7 visit.

**Visit 2: Day 7 ( $\pm 1$ ): Serology and Diary Card review**

The following activities will be carried out on day 7 and recorded in the CRF:

1. Collect and review the 1st Immunisation Diary Card, including new medication/analgesia/antipyretics taken during the preceding week (concomitant medication).
2. Remind subject to notify study personnel immediately if the subject experiences a SAE.
3. Collect 10ml clotted blood for serology. Process blood and store serum.
4. Schedule the Day 14 visit.

**Visit 3: Day 14 ( $\pm 2$ ): Serology**

The following activities will be carried out on day 14 and recorded in the CRF:

1. Collect 10ml clotted blood for serology. Process blood and store serum.
2. Remind subject to notify study personnel immediately if the subject experiences a SAE.
3. Schedule the Day 21 visit.

**Visit 4: Day 21 (+2): Second vaccination**

The following activities will be carried out on day 21 and recorded in the CRF:

1. Collect 10ml clotted blood for serology. Process blood and store serum.
2. For females of childbearing potential, perform a urine pregnancy test.
3. Check if the subject has taken an analgesic/antipyretic medication on Day 21 prior to study vaccination. Document this information on the subject's appropriate CRF.
4. Record oral temperature.
5. The vaccine administrator will give the same type of vaccine as before by IM injection in the deltoid muscle of the upper non-dominant arm.
6. Examine the site of injection of the vaccine for local reactions at the end of 30 minutes. These findings and any systemic reactions will be recorded on the appropriate CRF page.
7. Remind each subject in the evaluation of local and systemic reactions (e.g. how to measure the maximum diameter of induration and erythema in millimetres at the injection site and how to record temperature with a thermometer).
8. Give the second diary card. Tell subjects to:
  - Complete the diary at approximately the same time each day and to return it at the next visit;
  - Notify study personnel immediately if the subject experiences a SAE. Serious adverse events are defined in Sections 1.2 and 8.5.
  - Return the diary card to the site on the Day 28 visit.
9. Schedule the Day 28 visit.

**Visit 5: Day 28 (+2): Serology and Diary Card review**

The following activities will be carried out on day 28 and recorded in the CRF:

1. Collect and review the 2nd Immunisation Diary Card, including new medication/analgesia/antipyretics taken during the preceding week (concomitant medication).
2. Remind subject to notify study personnel immediately if the subject experiences a SAE.
3. Collect 10ml clotted blood for serology. Process blood and store serum.
4. Schedule the Day 35 visit.

**Visit 6: Day 35 (+3): Serology**

The following activities will be carried out on day 35 and recorded in the CRF:

1. Collect 10ml clotted blood for serology. Process blood and store serum.
2. Remind subject to notify study personnel immediately if the subject experiences a SAE.
3. Schedule the Day 42 visit.

**Visit 7: Day 42 (+3): Serology**

The following activities will be carried out on day 42 and recorded in the CRF:

1. Collect 10ml clotted blood for serology. Process blood and store serum.
2. Remind subject to notify study personnel immediately if the subject experiences a SAE.

3. Schedule the Day 180 visit.

### **Visit 8: Day 180 ( $\pm 10$ ): Study termination**

The following activities will be carried out on day 180 and recorded in the CRF:

1. Collect 10ml clotted blood for serology. Process blood and store serum.
2. Ensure Completion of all study termination CRFs.

### **8.2 Processing of samples for serology**

At least 10 mL serum should be available for immunogenicity assays (HI, MN, and possibly SRH). On each of the scheduled days requiring serum samples, the clotted blood will be stored at 2°C to 8°C and centrifuged within 24 hours. Sera will be stored in triplicate in cryovials, with all cryovials labelled with the volunteer's trial code number, and day of collection. Samples should be stored frozen (below -14°C) until shipment.

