doses met all three CHMP licensing criteria. Further studies showed improved antibody persistence with MF59 containing vaccine, improved immune responses to other clades of H5 virus, and significantly higher antibody responses on boosting.

Leroux-Roels *et al.* evaluated A/Vietnam/1194/2004 (H5N1) vaccine manufactured by GlaxoSmithKline at doses of 3.8µg, 7.5µg, 15µg and 30µg HA with and without its proprietary AS03 adjuvant. The adjuvanted formulations were significantly more immunogenic than the non-adjuvanted formulations at all antigen doses. At the lowest antigenic dose, immune responses for the adjuvanted vaccine against the vaccine strain met or exceeded all US Food and Drug administration and EU CHMP licensure criteria. Further research showed broad cross-clade immune responses at the lowest antigen dose (3.8µg) with adjuvant, but no cross-clade response in the non-adjuvanted group.

**Reproducibility of the serology assays for influenza** For research purposes and vaccine licensure, influenza vaccines are evaluated by clinical trials that assess immunogenicity by the presence of serum antibody. Collaborative studies have shown that the serology assays are highly variable between laboratories – with variability between laboratories for HI assays varying by up to 32-fold. This leads to difficulties in interpreting results from different manufacturers. At the 5th WHO Meeting on Evaluation of Pandemic Influenza Prototype Vaccines in Clinical Trials, 12-13 February 2009, WHO highlighted the need for standardised assays and internationally accepted antiserum standards.

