#### B. ONLY ONE VACCINE ARRIVES AT EACH CENTRE PRIOR TO REGULATORY APPROVAL:

This scenario is the one most likely to occur. It will be implemented if all regulatory approval is in place, AND only one of the two trial vaccines is available in each centre, AND the second vaccine will not arrive within five days of arrival of the first vaccine. Subjects who meet the study admission criteria will be enrolled into the study and will be assigned a **5 digit subject number**:

As before the statistician would generate three 'randomisation' lists for each centre, with a list for each age band.

As before, the first digit identifies the study site (1 for Leicester; 2 for Nottingham; 3 for Sheffield);  
As before, the second digit reflects the age of the subjects on Day 0 (1 for 18-44; 5 for 45-64; and 9 for 65 years and older);

As before the next three digits identify the subject within the site.

HOWEVER, the distribution of the numbers will be randomised, with the first 60 numbers corresponding to the first vaccine to arrive (Vaccine 1), and the second 60 numbers corresponding to the second vaccine (Vaccine 2).

As an example, the first person to be vaccinated in Leicester could have the number 10054, i.e., with '1' corresponding to Leicester, '0' reflecting that he/she is aged 18-44 years, and '054' being the volunteer's unique trial number.

Each centre will continue recruiting volunteers within an age band until the tally for the centres reaches a total of 60 subjects for that age band for Vaccine 1. The same process will then be carried out with Vaccine 2, when it arrives.

Depending on the interval between arrival of GSK and Baxter vaccines, we will endeavour to ship sera from some volunteers who received Vaccine 2 in the first tranche of sera that was sent for analysis. The laboratory staff will not know when Vaccine 2 arrived and was first given, so will not know whether sera were collected from recipients of GSK or Baxter vaccine.

Vaccinees will not be told which vaccine they receive. They will be instructed to look away, both during preparation and administration of the vaccine. It is essential that volunteers do not see the syringe that is used or whether the vaccine is translucent or cloudy.

As before, only one study nurse/doctor will be responsible for vaccine administration in each centre. This study nurse/doctor will be un-blinded with respect to the type of vaccine administered; he/she will play no other role in the study.

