**9.2.4 Analysis of immunogenicity criteria**

Blood samples for immunogenicity assays will be collected on Days 0 (prevaccination), 7, 14, 21, 28, 35, 42, and 180.

Antibody response will be evaluated by haemagglutination inhibition (HI), neutralization (MN), and possibly single-radial haemolysis (SRH) in all subjects.

HI and/or MN antibody titres need to be assessed rapidly and so will be analysed in three tranches:

- 1st tranche of sera measuring antibodies before and after 1st injection: Days 0, 7, 14, and 21
- 2nd tranche of sera measuring antibodies before and after 2nd injection: Days 21, 28, 35, and 42.
- 3rd tranche of sera measuring persistence of antibodies: Days 0, 42 and 180.

HI and MN assays will be performed at the Health Protection Agency Centre for Infections, Enteric, Respiratory & Neurological Virus Laboratory, London, UK. SRH tests may be done at the National Institute for Biological Standards and Control. Antibody titrations will be done in duplicate. Pre- and post-vaccination samples from each person will be titrated simultaneously, as specified in the CHMP guidance. The titre assigned will be the geometric mean of two independent determinations.

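### Serum vials carry the day of collection and the protocol states no laboratory masking to time point, an avoidable risk to a verdict against fixed licensing limits

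*Protocol*

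**What the plan says.** Section 8.2 has sera stored in triplicate, each vial bearing the subject's "trial code number, and day of collection". The next step is storage: "Samples should be stored frozen (below -14°C) until shipment". No recoding between the site freezer and the laboratory bench is described.

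Section 9.2.4 sets out the assay work. "Pre- and post-vaccination samples from each person will be titrated simultaneously, as specified in the CHMP guidance". Titrations are in duplicate: "The titre assigned will be the geometric mean of two independent determinations". Sera are assayed in three tranches:
- tranche 1: Days 0, 7, 14 and 21;
- tranche 2: Days 21, 28, 35 and 42;
- tranche 3: Days 0, 42 and 180.

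Laboratory masking appears once, in section 7.4 under scenario B (one vaccine arrives first). Laboratory staff are not to learn when the second vaccine came into use, "so will not know whether sera were collected from recipients of GSK or Baxter vaccine". That concerns vaccine type. Nothing in the protocol masks the laboratory to time point.

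Section 9.2.5.1 judges each vaccine against fixed limits 21 days after the second dose, and all three must be met. At ages 18-60 they are seroconversion or significant rise above 40%, geometric mean increase above 2.5, and HI titre of at least 40 in more than 70%. Over 60 the limits are 30%, 2.0 and 60%.

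**The concern.** The protocol guards against the laboratory guessing which vaccine a serum came from, but its labelling rule reveals which visit it came from. Whether the day on the label is a study day or a calendar date, it puts one person's vials in order and so identifies the baseline.

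Masking to vaccine protects a comparison between vaccines, because an expectation effect that ignores vaccine falls on both arms alike. It does not protect the primary verdict, which has no comparator. Two of the three criteria are within-person changes from baseline, and the third is a post-vaccination threshold. Reading later sera a step high, or baseline sera a step low, moves results towards a pass for both vaccines. The same applies to the secondary question of whether one dose is enough, which rests on Day 21 and is meant to inform vaccination strategy.

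**Working it through.** **Where the time point is open, by tranche (sections 8.2 and 9.2.4 read together)**

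| Tranche | Days | Day 0 present? | How the time point shows |
|---|---|---|---|
| 1 | 0, 7, 14, 21 | Yes | Side by side and by label; serves the one-dose question |
| 2 | 21, 28, 35, 42 | No | By label alone; first reading of the Day 42 sera used for the primary verdict |
| 3 | 0, 42, 180 | Yes | Side by side and by label |

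The protocol gives no figure for reading bias, so there is none to reproduce. What follows is illustration.

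**Seroprotection**

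Assumed inputs: 55 evaluable per group (between the 50 required and the 60 recruited in section 9.2.1), true seroprotection 66%, log2 titres normal with SD 1.9 two-fold steps. The 70% limit at HI 40 is from section 9.2.5.1.

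1. z with Φ(z) = 0.66 is 0.412.
2. Share reading 20 = Φ(-0.412) - Φ(-0.412 - 1/1.9) = 0.340 - 0.174 = 0.166.
3. Passing means more than 0.70 × 55 = 38.5, so at least 39 of 55. At a true rate of 0.66 the binomial probability is 0.27.
4. Let q be the chance that a reading of 20 is called 40. The assigned titre is the geometric mean of two readings. One raised reading gives √(20 × 40) = 28.3, still below 40, so both must be raised to cross. This takes the two readings to agree at 20 before any raising.
   - Raised together: rate = 0.66 + 0.166q.
   - Raised independently: rate = 0.66 + 0.166q².

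| q | Rate, together | P(pass) | Rate, independent | P(pass) |
|---|---|---|---|---|
| 0 | 66.0% | 0.27 | 66.0% | 0.27 |
| 10% | 67.7% | 0.36 | 66.2% | 0.28 |
| 20% | 69.3% | 0.46 | 66.7% | 0.30 |
| 30% | 71.0% | 0.57 | 67.5% | 0.35 |

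5. Away from the limit little changes. By the same method, even with both readings raised at q = 30%, a true rate of 50% (20.1% reading 20) moves the pass probability only from 0.001 to 0.017. A true rate of 85% passes with probability above 0.99 either way.

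**Rise criteria**

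If each post-vaccination reading is called one dilution high with probability q, the mean log2 titre rises by q. This holds whether the duplicates move together or independently, because a geometric mean averages logs. The geometric mean increase is multiplied by 2^q: 1.07 at q = 10% and 1.19 at q = 25%.

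For seroconversion, a simulation of 400,000 subjects assumed baseline titres centred on 8 (SD 1 log2), a mean rise of 1.7 log2 (SD 1.6), and a share q of assigned post-vaccination titres raised one full dilution. A rate of 34.9% then reads as 37.1% at q = 10% and 40.3% at q = 25%. That is about 2 to 5 points near the 40% limit, with duplicates in effect raised together.

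**The case against.** **The protocol does not say that readers see the day.** Section 8.2 covers site processing up to shipment. The laboratory may re-accession sera under its own procedure, which is not at hand. This stands: a reader might infer that staff know which serum is which, but the documents support only that no masking to time point is stated.

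**Nothing shows that expectation shifts end-points.** This also stands. The reading tendency and its rate are assumptions, and a reader who infers that the trial's results are biased goes beyond the documents.

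**Duplicate titration is a safeguard.** It is, for the threshold criterion: it cuts 36-57% to 28-35% when readings agree beforehand and are raised independently. It gives less protection if duplicates often disagree, or if both are read with the same expectation, and it does not protect the mean fold rise.

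**Side-by-side reading is not the first route to the primary verdict.** Correct. Day 42 is first read in tranche 2 without a Day 0 serum, and the two are paired only in tranche 3. The label shows the time point in every tranche.

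**Assay variability is not evidence here.** A reader might lean on the background section's remark about HI assays, "with variability between laboratories for HI assays varying by up to 32-fold". That figure is between laboratories, whereas section 9.2.4 runs all HI and MN assays in one. It says nothing about reading bias within a laboratory and is not relied on.

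**Simultaneous titration follows the cited guidance.** Agreed, and nothing here argues against it.

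**Conclusion.** The point holds as a design weakness. As written, the labels reveal the time point, no passage masks the laboratory to it, and the primary verdict is of a kind in which a common upward shift would not cancel. It is a risk and not a demonstrated bias, and it depends on the laboratory not recoding the sera.

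The size depends on assumptions that the protocol cannot settle: how often a reading is raised, whether duplicates move together, and how close a group lies to a limit. The base case of 66% against a 70% limit was placed where the pass probability is sensitive. There the chance of passing rises from 27% to somewhere between 28% and 57%; well away from a limit the effect is negligible. This merits a cheap improvement and does not make the trial's conclusions unsafe.

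**What to change.** - **Section 8.2:** send tubes to the laboratory under a coded accession number that hides the visit day, with the key held at the trial office. Supply each person's sera for a tranche as a coded set in random order, so that simultaneous titration is kept.
- **Section 9.2.4:** state that assay readers are masked to both time point and vaccine until the titres of each tranche are locked, whichever allocation scenario in section 7.4 applies.
- If the laboratory already recodes sera on receipt, one sentence saying so in either section closes the point.

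The cost is label printing, a pull list for each tranche, slightly more sample tracking, and a small risk of mix-up, which the key controls. Sample size, visits and assays are unchanged.

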### **8.3 Diary cards**

Diary cards will be issued to all subjects instructing them to record their temperature and local and systemic symptoms at 6 and 24 hours after vaccination, and then daily for a total of 7 days, or longer should symptoms persist.

Information will be sought concerning the presence or absence of: redness at the injection site; local itching; local swelling; ulceration at the injection site; local pain; warm feeling at the injection site; tenderness to touch at the injection site; limitation of the use of the arm; headache; nausea; dizziness; diminished appetite; breathlessness; cough; coryza; wheeze; skin rash; generalised itching; fatigue; 'other' symptoms, use of antipyretic/relief medication and any changes in medication.

Subjects will score the severity of symptoms and effect on daily activities ranging from 0 (symptom absent), 1 (symptom occurred but not often or severe enough to cause inconvenience), 2 (symptom occurred often and severe enough to interfere with daily activities and requires no medical intervention), 3 (symptom occurred often, severe enough to markedly interfere with daily activities; requires medical intervention).

Subjects will also be asked to document any unsolicited symptoms.

Subjects will be instructed that in the event of any serious adverse event, he/she must notify the investigator immediately and be reviewed clinically. Serious adverse events are defined in (see Definitions (Sections 1.2 and 8.5).

### **8.4 Local and systemic reactions**

The occurrence of selected indicators of reactogenicity (listed below), which by definition, can only occur up to 6 days post-vaccination, will be recorded on the Local and Systemic Reactions CRF rather than the Adverse Events CRF:

- **Local Reactions:** Ecchymosis, erythema, induration, swelling and pain at injection site;

- **Systemic Reactions:** Chills, malaise, myalgia, arthralgia, nausea, headache, sweating and fatigue;
- **Other indicators of reactogenicity:** Stayed at home due to reactions, oral temperature and use of analgesic/antipyretic medication.

